**1.2.2. Rationale for the study design**

Only the subjects included in STEP 2 of the primary vaccination study (NTHi-Mcat-001/ 201281) will be enrolled in this follow-up study. These study groups were chosen because the subjects included reflect the primary age range (50-71 years at the time of enrolment) of the target population (COPD patients with a previous history of exacerbation). STEP 2 of the NTHi-Mcat-001 study included 90 healthy adults, 50–71 years old at the time of enrolment, with a smoking history of at least 10 pack-years, either receiving placebo control, or one of two AS01E adjuvanted formulations, i.e. 10  $\mu$ g of PD, 10  $\mu$ g of PE-PilA and 10  $\mu$ g of UspA2 (Group 10-10-10-AS) or 10  $\mu$ g of PD, 10  $\mu$ g of PE-PilA and 3.3  $\mu$ g of UspA2 (Group 10-10-3-AS) (30/group).

**1.3. Benefit: Risk Assessment**

Please refer to the current Investigator Brochure for the summary of potential risks and benefits of NTHi-Mcat investigational vaccine.

**CONFIDENTIAL**204913 (NTHI-MCAT-006 EXT:001)  
Protocol Amendment 1 Final

The following section outlines the risk assessment and mitigation strategy for this study protocol:

### 1.3.1. Risk Assessment

Important Potential/Identified Risk	Data/Rationale for Risk	Mitigation Strategy
Study Procedures		
Risk of blood sampling	Blood sampling associated risk of syncope, dizziness, infection at the site after or during venepuncture.	Blood samples will be obtained by a trained professional and medical assistance will be available.  The potential risk of feeling faint, or experiencing mild local pain, bruising, irritation or redness at the site where blood was taken, is mentioned in the ICF. The amount of blood to be taken for sampling will not be harmful to the subject's health.

### 1.3.2. Benefit Assessment

Benefits considerations include:

- Contribution to the process of developing a vaccine which reduces AECOPD.
- Medical evaluations/assessments associated with this study (i.e. physical examination).

### 1.3.3. Overall Benefit: Risk Conclusion

The balance of anticipated benefits and apparent risks associated with this long-term follow-up study are acceptable as there is no administration of NTHi-Mcat vaccine planned in this study and the risks from the study procedures are believed to be acceptable.

## 2. OBJECTIVE(S)

### 2.1. Primary objective

- To assess the persistence of humoral antibodies up to 3 years after the last planned visit (Month 14) in the NTHi-Mcat-001 study.

CONFIDENTIAL

[figure not shown]
204913 (NTHI-MCAT-006 EXT:001)  
Protocol Amendment 1 Final

## 2.2. Secondary objective

- To assess the safety of the investigational NTHi-Mcat vaccine in terms of serious adverse events and potential immune-mediated diseases up to 3 years after the last planned visit (Month 14) in the NTHi-Mcat-001 study.

## 3. STUDY DESIGN OVERVIEW

**Figure 1** Study design overview

BS H = blood sample for humoral immune responses;

Rando = randomisation; LV= Last Visit of NTHi-Mcat-001 study; V = Visit of NTHi-Mcat-006 study ; M = Month; VAC = vaccination (indicated in grey);

\* With a cigarette smoking history  $\geq 10$  pack-years (calculation pack-years = average number of cigarettes smoked per day  $\times$  number of years smoked)/20

Protocol waivers or exemptions are not allowed unless necessary for the management of immediate safety concerns. Therefore, adherence to the study design requirements, including those specified in the outline of study procedures (Section 5.5), are essential and required for study conduct.

- Experimental design: Phase I, controlled, multi-centric, single-country, long term follow-up study with three parallel groups from NTHi-Mcat-001 study.
- Duration of the study: For each subject, the study will last approximately 30 months.
- Epoch 001 : Long-term follow-up starting at Visit 1 (Month 20) and ending at Visit 6 (Month 50).
- Primary completion Date (PCD): last subject of Visit 6 (Month 50).

Refer to [glossary of terms](#) for the definition of PCD.

**CONFIDENTIAL**204913 (NTHI-MCAT-006 EXT:001)  
Protocol Amendment 1 Final

- End of Study (EoS): Last testing results released for samples collected at Visit 6.

Refer to [glossary of terms](#) for the definition of EoS.

- Study groups of NTHi-Mcat-001 study:

- **10-10-10-AS:** Up to 30 subjects who have received two doses of the AS01E-adjuvanted GSK Biologicals' NTHi-Mcat investigational vaccine during STEP 2 of NTHi-Mcat-001 study containing 10µg of PD, PE-PilA and UspA2.
- **10-10-3-AS :** Up to 30 subjects who have received two doses of the AS01E-adjuvanted GSK Biologicals' NTHi-Mcat investigational vaccine during STEP 2 of NTHi-Mcat-001 study containing 10µg of PD, 10µg of PE-PilA, and 3.3µg of UspA2.
- **PLACE2 :** Up to 30 subjects who have received two doses of placebo (saline solution) during STEP 2 of the NTHi-Mcat-001 study.

**Table 1 Study groups and epochs foreseen in the study**

Study groups*	Number of subjects	Epoch
		Epoch 001
10-10-10-AS	up to 30	x
10-10-3-AS	up to 30	x
PLACE2	up to 30	x

\*Study groups of NTHi-Mcat-001 study. No vaccinations will be administered in this trial.

- **Control:** placebo control.
- **Blinding:** This is a long-term follow-up study following up on the observer blinded NTHi-Mcat-001. Data from the NTHi-Mcat-001 study may still be blinded at the start of this study; therefore, at the time of enrolment, subjects may not be aware of the study group to which they were assigned in the NTHi-Mcat-001 study.
- **Sampling schedule:** Blood samples for humoral immunogenicity will be collected from all subjects at Visit 1 (Month 20), Visit 2 (Month 26), Visit 3 (Month 32), Visit 4 (Month 38), Visit 5 (Month 44) and Visit 6 (Month 50).
- **Type of study:** extension of other protocol(s) (NTHi-Mcat-001 [201281]).
- **Data collection:** Electronic Case Report Form (eCRF)
- **Safety monitoring:** Follow-up of Serious Adverse Events (SAEs) and potential immune-mediated diseases (pIMDs). Refer to Section 8.4 for detailed description of safety monitoring.

## 4. STUDY COHORT

### 4.1. Number of subjects/centres

A total of approximately 90 subjects who were exposed in STEP 2 of study NTHi-Mcat-001 (201281) and who agree to participate in the present study will be enrolled at the same study centres in Belgium.

**CONFIDENTIAL**204913 (NTHI-MCAT-006 EXT:001)  
Protocol Amendment 1 Final

Overview of the recruitment plan:

At the time of the initiation of this long term follow-up study, the investigator will contact all subjects who were enrolled in 10-10-10-AS, 10-10-3-AS and PLACE2 groups of study NTHI-Mcat-001 (201281) at the study centres in Belgium and who received a full vaccination course with the investigational vaccines.. The reason for non-participation in the long-term follow-up study will be documented in the site's screening log.

#### **4.2. Inclusion criteria for enrolment**

Deviations from inclusion criteria are not allowed because they can potentially jeopardize the scientific integrity, regulatory acceptability of the study or subject safety. Therefore, adherence to the criteria as specified in the protocol is essential.

All subjects must satisfy ALL the following criteria at study entry:

- Subjects who previously participated in STEP 2 of study NTHI-Mcat-001 (201281), and performed the last study visit (Month 14) and received the 2 study vaccinations.
- Subjects who, in the opinion of the investigator, can and will comply with the requirements of the protocol (e.g. return for follow-up visits). And subjects' Legally Acceptable Representative(s) [LAR(s)] who, in the opinion of the investigator, can and will comply, with the requirements of the protocol.
- Written informed consent obtained from the subject/ LAR(s) of the subject prior to performance of any study specific procedure.

#### **4.3. Exclusion criteria for enrolment**

Deviations from exclusion criteria are not allowed because they can potentially jeopardize the scientific integrity, regulatory acceptability of the study or subject safety. Therefore, adherence to the criteria as specified in the protocol is essential.

The following criteria should be checked at the time of study entry. If ANY exclusion criterion applies, the subject must not be included in the study:

- Use of any investigational or non-registered product (drug or vaccine) during the period starting 30 days before the first follow-up study visit (Month 19 to Month 20), or planned use during the study period.
- Chronic administration (defined as more than 14 days in total) of immunosuppressants or other immune-modifying drugs since the end of the NTHI-Mcat-001 study. For corticosteroids, this will mean prednisone  $\geq$  20 mg/day, or equivalent. Inhaled and topical steroids are allowed.
- Administration of long-acting immune-modifying drugs at any time during the study period (e.g. infliximab).

**CONFIDENTIAL**204913 (NTHI-MCAT-006 EXT:001)  
Protocol Amendment 1 Final

- Concurrently participating in another clinical study, at any time during the study period, in which the subject has been or will be exposed to an investigational or a non-investigational vaccine/product (pharmaceutical product or device).
- Administration of immunoglobulins and/or any blood products during the period starting 3 months before the first follow-up visit or planned administration during the study period.
- Current alcoholism and/or drug abuse.
- Has significant disease (including significant neurological or psychological disorders), in the opinion of the investigator, likely to interfere with the study and/or likely to cause death within the study duration.
- Any other condition that the investigator judges may interfere with study findings.

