#### **6.1.2. Concomitant medications/products/vaccines that may lead to the elimination of a subject from per-protocol analyses**

The use of the following concomitant medications/products/vaccines will not require withdrawal of the subject from the study but may determine a subject's evaluability in the per-protocol analysis. See Section 10.4 for cohorts to be analysed.

- Any investigational or non-registered product (drug or vaccine) used during the study period.
- Immunosuppressants or other immune-modifying drugs administered chronically (i.e. more than 14 days in total) during the study period. For corticosteroids, this will mean prednisone  $\geq$  20 mg/day (for adult subjects), or equivalent. Inhaled and topical steroids are allowed.
- Long-acting immune-modifying drugs administered at any time during the study period (e.g. infliximab).
- Immunoglobulins and/or any blood products administered during the study period.

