### **9.3. Screen and baseline failures**

Screening failures are defined as subjects who are withdrawn from the study after giving informed consent, but who do not meet the inclusion and exclusion criteria.

The following information will be collected for screening failures:

- Informed consent.
- Inclusion/exclusion criteria.
- Demographic data.
- SAEs related to study participation, to concomitant use of GSK products or any fatal SAEs.
- Screening conclusion.

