5.1.1. Exposed Set

The ES for safety analysis will include all subjects from STEP 2 of NTHI-Mcat-001 (201281) enrolled in this follow-up study.

The ES for immunogenicity analysis will include all subjects from STEP 2 of NTHI-Mcat-001 (201281) enrolled in this follow-up study and for whom immunogenicity data are available.

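### Entry criteria at about Month 20 can remove subjects because of a pIMD or SAE that arose after Month 14, yet the safety objective starts at Month 14 and the safety set holds enrolled subjects only

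*Protocol*

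**What the plan says.** **Window.** The secondary objective (Protocol 2.2, repeated in SAP 3.2) covers SAEs and "potential immune-mediated diseases up to 3 years after the last planned visit (Month 14) in the NTHi-Mcat-001 study". SAP 8.2 bases the secondary-objective analysis, at each interim and at the end, on safety data from the Month 14 visit onward.

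**Entry.** Protocol 4.3 applies its exclusions at study entry, about Month 20, and allows no deviation: "If ANY exclusion criterion applies, the subject must not be included in the study". Two criteria matter most here:
- "Chronic administration (defined as more than 14 days in total) of immunosuppressants or other immune-modifying drugs since the end of the NTHI-Mcat-001 study". Corticosteroids count from a stated systemic dose; inhaled and topical steroids do not count.
- "Has significant disease (including significant neurological or psychological disorders), in the opinion of the investigator, likely to interfere with the study", or likely to be fatal during the study.

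**Safety set.** SAP 5.1.1: "The ES for safety analysis will include all subjects from STEP 2 of NTHI-Mcat-001 (201281) enrolled in this follow-up study". Protocol 10.4.1 agrees, and SAP 11.2.4 uses enrolled subjects as the denominator.

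**Subjects not enrolled.** The only safety data kept on screening failures are "SAEs related to study participation, to concomitant use of GSK products or any fatal SAEs" (Protocol 9.3). Reasons for non-participation go into a site screening log (Protocol 4.1), and neither document plans an analysis of it.

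**Same drugs after entry.** Under Protocol 6.1.2 their use "will not require withdrawal of the subject from the study but may determine a subject's evaluability in the per-protocol analysis".

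**The concern.** Protocol 1.2.1 gives the adjuvanted formulation as the reason for continued pIMD monitoring. A subject who develops a disease from Protocol Table 7 after Month 14, and whose treatment meets the drug criterion before Visit 1, may not enter. A subject whose new disease is judged likely to interfere with the study may not enter either. In both cases the reason for exclusion can be the very event that the objective is meant to count, and the subject leaves both numerator and denominator.

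The drug criterion appears to serve the antibody read-out, since after entry the plan handles the same drugs through per-protocol status alone. Protection of subjects does not obviously explain it: no vaccine is given, and blood sampling is the only risk listed in Protocol 1.3.1. At stake is whether a report of few or no pIMDs can be stated for Month 14 to Month 50.

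**Working it through.** **Inputs.** Months 14, 20 and 50 (Protocol 2.2 and Table 2); 30 subjects per parent-study group, hence 2 × 30 = 60 vaccinated (Protocol 1.2.2); Clopper-Pearson exact intervals (SAP 11.1). The plan gives no expected event rate and no sample-size calculation (Protocol 10.3), so there is no stated figure to reproduce. Case counts below are assumptions.

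**Step 1: the windows.** Objective: 50 − 14 = 36 months. Follow-up from Visit 1: 50 − 20 = 30 months. Gap: 20 − 14 = 6 months, and 6/36 = 16.7%.

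**Step 2: what happens to an event.**

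| Situation | Result under the plan |
|---|---|
| Gap event; subject found ineligible before consent | Not enrolled; screening-log entry only. The retrospective collection of vaccine-related SAEs (Protocol 8.2.1) requires consent |
| Gap event; subject consents, then fails screening | Not in the safety set; a non-fatal pIMD is not among the items kept (Protocol 9.3) |
| Gap pIMD or SAE not judged vaccine-related; subject enrolled | Medical history (Protocol 5.6.4); pIMD and general SAE recording starts at Visit 1 (Protocol 8.2.1) |
| Gap SAE judged vaccine-related; subject enrolled | Collected retrospectively (Protocol 8.2.1) |
| Gap pIMD judged vaccine-related, reported after consent; subject enrolled | Included by SAP 6.3.1 |
| Event and treatment start after Visit 1 | Counted; the drug affects per-protocol status only (Protocol 6.1.2) |

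Two separate losses appear. Eligibility removes some subjects. The collection window drops most gap events even in subjects who are enrolled.

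**Step 3: share of events open to removal.** Assume a constant event rate, a look-back of L months, and a share q of events in that period meeting an exclusion. The share of all Month 14–50 events removed by eligibility is q × L/36. With L = 6 and q from 25% to 100%, this runs from 0.25 × 6/36 = 4.2% to 1 × 6/36 = 16.7%. For the drug criterion L may be smaller. It runs from the end of the parent study, which is not tied to the subject's Month 14 visit. The glossary lets End of Study fall up to 8 months after the last subject's last visit. As 8 exceeds 6, on that meaning L could shrink to zero.

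**Step 4: illustration.** The upper limit for 0/n is 1 − 0.025^(1/n). For x > 0 it is the 97.5th percentile of Beta(x + 1, n − x). No other events are assumed.

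| Subjects | Cases removed | If counted (95% CI) | As reported (95% CI) |
|---|---|---|---|
| 60 vaccinated | 1 | 1/60 = 1.7% (0.0–8.9%) | 0/59 (0–6.1%) |
| 60 vaccinated | 2 | 2/60 = 3.3% (0.4–11.5%) | 0/58 (0–6.2%) |
| 60 vaccinated | 3 | 3/60 = 5.0% (1.0–13.9%) | 0/57 (0–6.3%) |
| One group of 30 | 1 | 1/30 = 3.3% (0.1–17.2%) | 0/29 (0–11.9%) |

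By Step 2, the third column applies only to gap events that would be collected on enrolment: those judged vaccine-related, or all of them if collection is extended back to Month 14.

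**The case against.** The strongest objection is that eligibility is not the main leak. A reader might infer that enrolling an excluded subject would by itself turn 0/59 into 1/60. For a gap pIMD not judged vaccine-related it would give 0/60, because the condition goes to medical history. The endpoints (Protocol 10.2, SAP 4.2) are also worded for the study period, and on that reading the criteria select a healthier cohort rather than delete endpoint events. This stands, and the fix must therefore change the collection window too. It does not remove the point: the objective and SAP 8.2 both start at Month 14, and SAP 8.2 creates no new collection.

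A reader might also infer that the bias favours the vaccine or hides an imbalance. The documents do not support that. The same criteria apply to PLACE2, and losing placebo cases would make the vaccine look relatively worse. With no blinding procedure (Protocol 5.3), criteria that rest on investigator opinion could act differently by group, but nothing shows that they do. All analyses are descriptive (SAP 7).

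The trigger is also narrower than every treated immune-mediated disease. Disease managed without such drugs, for 14 days or less, or with topical or inhaled steroids only does not meet the drug criterion. The disease criterion needs likely interference or death, not a diagnosis alone. The criterion on long-acting drugs is worded for the study period, so by its wording it does not address the gap.

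Finally, the parent study's post-study reporting rules are not in these documents and may capture some events. Amendment 1 is dated June 2018 and its visit example uses a Visit 1 in August 2017, so enrolment may already have been complete.

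**Conclusion.** The point holds in limited form. The plan states a safety objective from Month 14, but its safety set is formed at about Month 20 by criteria that some pIMDs and SAEs can themselves trigger. Any such removal lowers the observed absolute risk. The size of the bias and its effect on the vaccine-placebo comparison cannot be known from the documents.

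For scale, eligibility could remove 4.2% to 16.7% of Month 14–50 events, assuming a constant rate, a full six-month look-back and 25% to 100% of gap events meeting an exclusion. A shorter drug look-back would reduce this. The numbers are small, but so is the cohort. With 60 vaccinated subjects, the chance of at least one case, 1 − (1 − p)^60, is 26%, 45%, 70% and 95% at assumed true risks p of 0.5%, 1%, 2% and 5%, so a single case may be the whole signal. The change should be made because it is cheap, and because the plan as written would otherwise support a Month 14–50 statement from a cohort partly selected on that outcome. It does not affect the validity of events recorded from Visit 1.

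**What to change.** 1. **Eligibility, if enrolment is still open.** Make the criteria in Protocol 4.3 on immunosuppressants or immune-modifying drugs, and on immunoglobulins or blood products, reasons for Per-Protocol Set elimination only, and enrol these subjects in the Exposed Set for safety. SAP code 2040 exists but is worded for use during the study period, so extend it to the pre-entry period.
2. **Collection window.** Reconcile Protocol 5.6.4, 8.2.1 and 10.2 with Protocol 2.2 and SAP 8.2: at Visit 1, record all SAEs and pIMDs with onset since Month 14, not only vaccine-related SAEs. Without this, change 1 does not bring most gap events into the count.
3. **Reporting.** From the screening log, tabulate by parent-study group all STEP 2 subjects not enrolled and the reasons, next to the SAE/pIMD table. Use aggregate counts, where consent allows.

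If 1 and 2 are no longer possible, do 3 and limit the safety conclusion to subjects eligible at Visit 1 and to events from Visit 1.

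**Cost.** Amendment wording, one extra table, and at most a few more subjects from a fixed pool of 90. More Exposed Set subjects would fall outside the Per-Protocol Set. In a group of 30, three such subjects with serology reach 3/30 = 10%, which triggers the second immunogenicity analysis (Protocol 10.6, SAP 6.2.1).

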## **5. CONDUCT OF THE STUDY**

### **5.1. Regulatory and ethical considerations, including the informed consent process**

The study will be conducted in accordance with all applicable regulatory requirements.

The study will be conducted in accordance with the ICH Guideline for GCP, all applicable subject privacy requirements and the guiding principles of the Declaration of Helsinki.

GSK will obtain favourable opinion/approval to conduct the study from the appropriate regulatory agency, in accordance with applicable regulatory requirements, prior to a site initiating the study in that country.

Conduct of the study includes, but is not limited to, the following:

- Independent Ethics Committee (IEC) review and favourable opinion/approval of study protocol and any subsequent amendments.
- Subject/LAR(s) informed consent, as appropriate.
- Investigator reporting requirements as stated in the protocol.

GSK will provide full details of the above procedures to the investigator, either verbally, in writing, or both.

Freely given and written or witnessed/ thumb printed informed consent must be obtained from each subject and/or each subject's LAR(s), as appropriate, prior to participation in the study.

GSK Biologicals will prepare a model Informed Consent Form (ICF) which will embody the ICH GCP and GSK Biologicals required elements. While it is strongly recommended that this model ICF is to be followed as closely as possible, the informed consent requirements given in this document are not intended to pre-empt any local regulations

**CONFIDENTIAL**204913 (NTHI-MCAT-006 EXT:001)  
Protocol Amendment 1 Final

which require additional information to be disclosed for informed consent to be legally effective. Clinical judgement, local regulations and requirements should guide the final structure and content of the local version of the ICF.

The investigator has the final responsibility for the final presentation of the ICF, respecting the mandatory requirements of local regulations. The ICF generated by the investigator with the assistance of the sponsor's representative must be acceptable to GSK Biologicals and be approved (along with the protocol, and any other necessary documentation) by the IRB/IEC.

## **5.2. Subject identification and randomisation**

### **5.2.1. Subject identification**

Subject identification numbers have been assigned sequentially to the subjects who have consented to participate in the parent trial, according to the range of subject identification numbers allocated to each study centre, but different identification numbers will be used for this follow-up.

